5. OBJECTIVES

5.1 *General Objective*

To evaluate differences in the response of weight, body composition and metabolic biochemical parameters among obese patients following a normoprotein low-fat controlled ketogenic diet compared to a balanced BIEM).

5.2 *Specific Objectives*

- Intra- and intergroup comparison of patient weight and BMI reduction between baseline and subsequent follow-up monitoring visits.
- To determine the percentage of patients with weight loss equal to or greater than 10% of initial weight and the time it took for patients to reach this figure.
- Evaluate the evolution of comorbidities associated with obesity (HT, hyperglycemia or diabetes, hypercholesterolemia, hypertriglyceridemia, apneas), control of clinical and analytical parameters and changes in medication during the weight loss process and during follow-up.
- To know the tolerability of the diet: Incidence of side effects during the development of the study,
- Safety of the intervention diet: appearance of analytical alterations, especially of the ionic profile, renal function and hepatic function, incidence of serious adverse events.
- Assess diet adherence and dropout rate and cause.
- To know patient satisfaction with the assigned nutritional program.

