7. METHODOLOGY

7.1. Study setting.

The study will be conducted in Mexico City under the sponsorship of Zélé® and in collaboration with the VIME Weight Loss and Wellness Center of Mexico. During the year 2021 and with follow-up for 24 months. An open call will be made through different media including social networks for the recruitment of patients who meet the inclusion criteria and must present themselves for a clinical evaluation in which pathological history, clinical status, heart rate, blood pressure, oxygenation and temperature will be recorded. Nutritional assessment in which anthropometry and multifrequency electrical bioimpedance analysis (MFBIA) will be performed to determine body composition. Patients will have to bring a Complete Blood Count, a biochemical profile that includes the following determinations: Fasting blood glucose, glycosylated hemoglobin, urea, creatinine and uric acid, cholesterol, triglycerides, LDL, HDL and VLDL, direct and indirect bilirubins, alanine and aspartate aminotransferases, gamma-glutamyl transferase and albumin, determination of serum electrolytes sodium, chloride, potassium, magnesium, phosphorus and calcium, Fasting Insulin , HOMA index calculation. In addition to a thyroid function panel and arterial blood gases. They will be instructed during recruitment for the studies to be performed in a clinical laboratory, under the current standardization and with standardized and perfectly calibrated automated equipment, and a request will be made to keep the vials of the patients' plasmas. Patients who meet all the inclusion criteria will be selected and will have an interview with the principal investigator in which they will sign their letter of commitment and informed consent, then they will be subjected to the randomization process with a 2:1 allocation for treatment and controls, respectively. Subsequently, they will be submitted to the two nutritional treatments and will be clinically evaluated every week and will receive nutritional, psycho emotional and physical activity counseling. At each visit, adverse effects, changes in clinical status will be recorded and the presence of ketone bodies in capillary blood will be determined with the Freestyle Abbott optium H β -Ketone (β -hydroxy-Butyric Acid) device; during nutritional counseling, MFBIA will be performed using the In-Body 570 body composition analyzer. When ketone body levels above 0.8 mmol/liter are detected, a new arterial blood gas analysis will be taken; for patients who do not have elevated ketone bodies, an arterial blood gas will be taken between the first and second week of treatment. A new biochemical profile determination will be performed when patients have lost 40% of their overweight or between 10 and 12 kg, whichever

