
occurs first. And new biochemical evaluations when the decrease of Ketone Bodies below 0.4 mmol/l is detected or when patients have reached a loss of 60 to 70% of their overweight and one more when they reach their weight loss goal. Subsequently, only clinical and nutritional follow-up will be given along with psycho-emotional support and physical activity advice every 3 months up to 12 months and every 6 months up to 24 months.

7.2 Study design.

Longitudinal, Prospective, Controlled Randomized Clinical Trial.

7.3 Study population.

Patients of either sex, between 18 and 60 years of age, with a body mass index (BMI) between 30 and 35 kg/m².

7.4 Sample.

The sample will be obtained by open call through social media and all patients who come with their clinical analysis and meet the inclusion criteria will be evaluated until the sample number is reached. In order to obtain 95% power in this Controlled Clinical Trial and with a 95% CI, a 3:1 case-control ratio is established, considering a 35% attrition rate, 56 cases and 32 controls will be included and subsequently crossed to become cases. (Calculated with EPIinfo STATCALC for sample size)

Two blinded arms are proposed for the physician and the patient.

Obese patients assigned to the low-fat normoprotein controlled ketogenic diet group.

Obese patients assigned to a balanced hypocaloric diet. And who will subsequently be subjected to a controlled normoproteic low-fat ketogenic diet.

7.5 Inclusion, exclusion and elimination criteria.

7.5.1 Inclusion:

- Men and Women
- 18 to 60 years of age
- With BMI between 30 and 35 Kg/m²
- Who has not taken weight loss treatment in the last 6 months

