7.5.2 Exclusion

- Pregnant or breastfeeding patients.
- Patients with severe eating disorders, alcoholism, or drug addiction.
- Patients with severe psychological disorders (e.g. schizophrenia, bipolar disorder).
- Patients with hepatic alteration defined as increase of ALT, AST, GGT more than 4 times the reference value.
- Patients with renal impairment defined as a glomerular filtration rate below 60 ml/min.
- Patients with type 1 or insulin-dependent DM, or DM2 on insulin therapy.
- Patients with obesity caused by endocrinological diseases (except type 2 DM).
- Patients with hemopathies.
- Cancer patients.
- Patients with active cardiovascular or cerebrovascular disease (heart rhythm disorders, recent infarction [<6m], unstable angina, decompensated heart failure, recent vascular accident [<6m]).
- Patients with gout.
- Patients with renal lithiasis.
- Patients with cholelithiasis.
- Patients with depression.
- Patients with electrolyte disorders.

- Patients with orthostatic hypotension.
- Patients with an altered or abnormal electrocardiogram.

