7.5.3 Elimination criteria

- Patients who drop out and decide to stop participating in the study.

(The patient has the right to withdraw from the study at any time, without the need to offer any explanation and without affecting the patient's future care or health care).

- The patient may also be withdrawn from the study at any time at the discretion of the investigator or the sponsor, for administrative or behavioral reasons or for missing two consecutive follow-up visits.
- Patients who during follow-up present any of the following criteria: Any serious adverse event
- Incoercible vomiting and nausea that do not allow following an oral diet.
- Worsening of diabetes control in patients with type II diabetes mellitus or insulin resistance
- Uncontrolled hypertension (SBP > 150 mmHg or SBP < 90 mmHg in successive repetitions).
- The reasons for abandonment of the study must be clearly documented in the registration notes. Any adverse reactions will be immediately reported to the Pharmaco-Surveillance system in charge of [name] [name] Principal Investigator.

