7.10 Description of treatments

7.10.1 Low-fat normoprotein Controlled Ketogenic Diet.

Patients randomly assigned to this group will undergo a standardized weight loss program under a nutritional intervention, physical exercise plan and emotional support.

The nutritional intervention is based on commercial preparations adjusted to 6 different stages.

Frank ketosis: the initial diet will consist of a very low calorie ketogenic diet (between 650 and 730 kcal/day) in 5 meal times, based on commercial and vegetable preparations with low glycemic index, an average of 1.2 g of protein/kg of ideal weight/day, 20 g/day of lipids based on essential fatty acids and less than 60 g/day of absorbable carbohydrates. Patients will also receive vitamin and trace element supplements (sodium chloride, magnesium oxide, calcium carbonate) to cover the daily requirements recommended for this type of diet. There is no stipulated time for this nutritional

intervention, the advance to the next stage is proposed as soon as the patient has lost 50% of his or her excess weight.

Mixed Ketosis: in this stage, one or two intakes of commercial preparations will be progressively replaced by proteins of natural origin (meat, fish, eggs, etc.), which will discreetly increase by 100 to 150 Kcal/day, without the patient 26.

Leaving the state of ketosis, the supplementation of vitamins and minerals will continue until the patient reaches 70% loss of excess weight.

Transition Stage: In this stage simple carbohydrates based on fruit and some complex carbohydrates in the form of cereals are added to the previous program, which allows the exit from the state of ketosis to enter a controlled hypocaloric diet of approximately 1300 to 1500 kcal/day to metabolically readapt to the consumption of macronutrients in an approximate proportion of 30 to 35% protein, 25% fat and 40 to 45 % carbohydrates. Patients will receive vitamin supplements to cover daily needs. Weight loss is not expected at this stage due to its short duration.

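### Entry criteria set no resting blood pressure limit, yet follow-up removes patients for SBP above 150 or below 90 mmHg, so a value persistent at screening can lead to randomisation and then removal

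*Combined protocol and SAP*

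**What the plan says.** **Entry.** The inclusion list in 7.5.1 covers sex, age, BMI and recent treatment ("Who has not taken weight loss treatment in the last 6 months"). It has no blood pressure item. The exclusion list in 7.5.2 does not name hypertension and gives no resting limit. Its nearest items are "Patients with orthostatic hypotension", a defined list of active cardiovascular and cerebrovascular conditions, and an abnormal electrocardiogram.

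**Screening.** Section 7.1 provides for a "clinical evaluation in which pathological history, clinical status, heart rate, blood pressure, oxygenation and temperature will be recorded". No eligibility decision is tied to the blood pressure reading.

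**Objectives.** Section 5.2 sets out to "Evaluate the evolution of comorbidities associated with obesity (HT, hyperglycemia or diabetes" and other conditions, so hypertensive patients are expected in the trial.

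**Removal.** Section 7.5.3 applies to "Patients who during follow-up present any of the following criteria", and one of these is "Uncontrolled hypertension (SBP > 150 mmHg or SBP < 90 mmHg in successive repetitions". The limits are absolute, and the number of repetitions is not given.

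**Treatment and size.** In the ketogenic arm (7.10.1), "the initial diet will consist of a very low calorie ketogenic diet (between 650 and 730 kcal/day"). Section 7.4 states: "considering a 35% attrition rate, 56 cases and 32 controls will be included".

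**The concern.** The plan treats SBP persistently above 150 or below 90 mmHg as incompatible with staying in the study, but does not check for it at entry. A patient who already has such a value can pass every written entry criterion, be randomised, and meet the removal rule at the first successive repeats with no change in condition. A patient who improves from 170 to 155 mmHg meets it too. The neighbouring diabetes rule in 7.5.3 differs, because it asks for a worsening.

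Three things are at stake:

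- **Randomised places.** Before randomisation, screening such a patient out costs no randomised place. Afterwards the same decision is a post-randomisation loss, and 7.9 does not say how removed patients are analysed.
- **Exposure.** In the ketogenic arm, a patient the plan would then remove is first started on a very low calorie diet.
- **Balance.** If one diet lowers blood pressure sooner, these removals could fall unequally between the arms. The documents do not establish that this happens.

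**Working it through.** **1. Do the written rules allow it?** Take a patient aged 45 with BMI 32, resting SBP persistently 160 mmHg, a normal ECG and no other disease.

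- 7.5.1: meets every item.
- 7.5.2: no item applies. Orthostatic hypotension is a postural fall, and the cardiovascular list does not include hypertension.
- 7.1: blood pressure is recorded, and the patient is randomised.
- 7.5.3: 160 exceeds 150 on successive repeats, so the patient is removed unless pressure has fallen.

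Investigator discretion appears in 7.5.3, but it concerns withdrawal, not entry. Nothing else in the document closes the gap.

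**2. How many patients?** The plan gives no figure to reproduce. From the document: 56 + 32 = 88 patients, and 0.35 × 88 = 30.8 expected losses. Assumed, because the document gives no SBP distribution: normal readings with mean μ and SD σ of 125 and 14, or 130 and 15 mmHg, and equal between-reading correlation r of 0.5 to 0.8.

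One reading above 150:

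- z = (150 − 125)/14 = 1.79, which gives 3.7%; × 88 = 3.3.
- z = (150 − 130)/15 = 1.33, which gives 9.1%; × 88 = 8.0.

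For k readings all above 150, let p(u) = 1 − Φ[(150 − μ − σ√r·u) / (σ√(1 − r))] and P(k) = ∫ p(u)^k φ(u) du. P(2) describes two screening readings. P(4) describes those two plus one given later pair, with no change in mean pressure.

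| μ / σ | r | P(2) | × 88 | P(4) | × 88 | P(4)/P(2) |
|---|---|---|---|---|---|---|
| 125 / 14 | 0.5 | 0.80% | 0.7 | 0.15% | 0.13 | 0.19 |
| 125 / 14 | 0.8 | 1.74% | 1.5 | 0.87% | 0.77 | 0.50 |
| 130 / 15 | 0.5 | 2.84% | 2.5 | 0.77% | 0.68 | 0.27 |
| 130 / 15 | 0.8 | 5.04% | 4.4 | 2.89% | 2.55 | 0.57 |

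The lower limit adds little: 0.03 to 0.19 of 88 fall below 90 on two readings.

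**3. Repeated visits.** Visits are weekly (7.1, 7.7), so one later pair understates the chance of removal. Take 12 weekly visits with one reading each, and remove a patient at the first two consecutive readings above 150. Given u, readings are independent, so the chance of such a run follows from p(u) by recursion. It is then weighted by p(u)² φ(u) and divided by P(2). With no change in mean pressure, about 62% to 92% of those above 150 on both screening readings would be removed. If mean pressure is 10 mmHg lower at all 12 visits, the range is 18% to 47%.

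No allowance is made for the ECG, renal and cardiovascular exclusions, which may lower all these counts.

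**The case against.** Entry and stopping rules serve different purposes, and nothing requires a stopping threshold to be repeated at entry. The open entry may be deliberate. Section 5.2 follows hypertension and medication changes, and H3 in Section 6 concerns metabolic syndrome. Patients with the highest pressure have the most room to improve, and they are the ones the fix screens out.

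The numbers are small and assumed. Three of the four scenarios avert less than one removal per 88 on a given later pair. At r = 0.5, 73% to 81% of those screened out would not meet the rule on that pair. Assuming no fall in pressure also favours the concern. With a 5 mmHg fall, the averted removals on that pair become 0.06 to 1.5 of 88, and with 10 mmHg 0.02 to 0.76. The existing exclusions and the pre-randomisation interview would catch some of these patients.

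Much of this stands. It limits the size of the problem, and the loss of some informative high-pressure patients is a real cost. It does not remove the gap. None of the safeguards sets a pressure limit, weekly visits give the rule many chances to act, and a patient removed early contributes little to the hypertension objective.

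**Conclusion.** The concern holds on the text. The entry criteria admit patients whose persistent resting SBP already meets the plan's own removal limit, and the screening reading that would identify them is not used. Both sets of rules can be followed as written, so this is a misalignment and not a contradiction.

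Its effect on the trial's conclusions is small. Even the highest scenario, 4.4 of 88 above 150 on two readings, is well below the planned loss of about 31, and the low-pressure limit is negligible. That some patients could be affected follows from the criteria alone. How many rests entirely on the assumed SBP distribution and correlation, and on how far pressure falls on treatment. Unequal loss between arms is possible but not shown. The change is worth making because it is cheap, not because the trial depends on it.

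**What to change.** Add one exclusion to 7.5.2: resting SBP above 150 or below 90 mmHg, confirmed on a stated number of readings (for example two) at the screening evaluation before randomisation. State the same number of readings in 7.5.3, so that all control centres apply the removal rule alike. Hypertensive patients within the limits stay eligible, so the comorbidity objective is kept.

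The cost is one line of text, a stated number of readings, and possibly one extra reading at a visit where blood pressure is already taken. About 1 to 4 candidates per 88 would be screened out, and some of them might have stayed in the trial. The change reduces blood pressure removals but does not end them: a patient at 145 mmHg at screening can still exceed 150 later.

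If the sponsor wants to keep patients with high baseline pressure, the alternative is to define removal in 7.5.3 relative to baseline. That keeps them in the trial, but it also means starting the very low calorie diet in patients above the present limit, so it should be a deliberate clinical decision.

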7.6 Variables

Variable name	Conceptual definition	Operational definition	Type of variable and measurement scale	Instrument for measurement
Clinical Variables				
Age	Life span of a person from birth to a given point in time	Age expressed by the patient during interrogation	Quantitative, Ratio, years.	Interrogation Registration form. Identification form section
Sex	Anatomical features that differentiate men from women	Sex expressed by the patient during interrogation	Qualitative Nominal, Male, Female	Interrogation Registration form. Identification form section
Weight	Mass of an individual expressed in kilograms	kg measurement with clinical scales	Quantitative, Ratio, Unit Kg, Minimum 20 Maximum 350	Data recording form, using In-Body electronic scales
Size	Distance from the floor to the crown of the head with the body resting on a flat surface and fully extended.	Standing height measurement, without shoes, with a calibrated stadiometer.	Quantitative, Ratio, Unit cm Min. 100, Max. 270,	Data recording form, using a
Blood Pressure	It represents the pressure exerted by the force of the heartbeat on the resistance of the arterial walls.	It is commonly measured with an ESFIGMOMANOMETRE R in the upper arm at the brachial artery.	Quantitative, Ratio, Unit mmHg. Min. 60-80, Max. 120-180	Data recording form, using a sphygmomanometer.
Heart Rate	Number of times the ventricles of the heart contract per unit of time, usually minute.	Number of beats per minute.	Quantitative, Ratio, Unit l/minute. Minimum 48, Maximum 120	Data registration form Measurement with digital monitor.
SaO2	Determination of O2 saturation in hemoglobin, through a non-invasive oximeter using pulse oximetry.	Oxygen saturation percentage	Quantitative, Ratio, % Saturation, Minimum 90%, maximum 150%.	Registration Form pulse oximetry using a noninvasive oximeter.

Body temperature	Property of bodies that determines the direction of heat flow produced by the energy released from the motion of atomic particles.	Measuring the heat level of a human	Quantitative, Ratio, Degrees Celsius Minimum 35.5 Maximum 42.0	Data Registration Form. Digital thermometer.
Body Composition Variables				
BMI	Indicator of body density determined by the ratio of body weight to body height.	BMI falls into these categories: below 18.5 (underweight); 18.5-24.9 (normal); 25.0-29.9 (overweight); 30.0 and above (obese).	Quantitative, Ratio, $BMI = \frac{\text{weight (kg)}}{\text{height squared (m}^2\text{)}}.$ Unit Kg/m ² , Minimum 11, Maximum 75	Data registration form,
Muscle Mass	Volume of total body tissue corresponding to muscle. ,	From the point of view of body composition, it corresponds to lean mass.	Quantitative, Ratio. Unit Kg. Minimum 10 Maximum 150	Data registration form Multi-frequency Bioelectrical Impedance Equipment
Fat Mass	Percentage of body weight made up of adipose tissue	Amount of fat in the body	Quantitative, proportion, Unit Percentage. Minimum 9 Maximum 80	Data registration form Multi-frequency Bioelectrical Impedance Equipment
Visceral Fat	Fatty tissue within the abdominal cavity, which includes visceral fat and retroperitoneal fat.	It is the most metabolically active fat in the body. Its increase is associated with metabolic complications of obesity.	Quantitative, Ratio. Unit Index. From 1 to 40	Data registration form Multi-frequency Bioelectrical Impedance Equipment
Bone Mass	Measurement of the amount of minerals (usually calcium and phosphorus) contained in the bones.	Skeletal weight	Quantitative, Ratio Unit Kg. From 1 to 7 kg.	Data registration form Multi-frequency Bioelectrical Impedance Equipment
Total body water	Amount of liquids, mainly water, found inside the body.	Percentage of the body that corresponds to water	Quantitative Proportion. Unit % and/or Kg. 0 a 150	Data registration form Multi-frequency Bioelectrical

				Impedance Equipment
Waist circumference	Measurement established at mid-armpit, at the point between the bottom of the last rib and the highest part of the hip.	Measurement made with a tape measure directly on the skin (without clothing). It will be measured at the height of the middle of the armpit, at the point between the bottom of the last rib and the highest part of the hip.	Unit Cm , Minimum 30 , Maximum 200	Registration form. Using tape measure
Hip circumference	specific anthropometric measurement for hip circumference measurement	Circumference of the widest part above the buttocks. Minimum 30, Maximum 200	Quantitative, Ratio Unit cm.	Recording format, measuring with tape measure.
Muscular Strength	The hand grip force measured by	Isometric muscle strength in the dominant hand	Quantitative Ratio Kg/Strength	Registration Form Digital dynamometer.
Blood Ketones	The blood ketone test measures the level of butyrate (ketones) in the blood.	Ketone bodies are substances produced by the body when cells do not receive enough glucose.	Quantitative, Ratio Unit mmol/liter Minimum 0.01 Maximum 25	Registration Form Abbott Ketone Test
Biochemical and Metabolic Variables				
Hb	Oxygen Transporting Protein in erythrocytes	Oxygen Transporting Protein in erythrocytes	Quantitative Ratio. Gr/l. minimum 10 maximum 16	Registration format. Clinical laboratory determination
Hto	Proportion of formed elements in the blood	Proportion of formed elements in the blood	Quantitative Ratio minimum 27 Maximum 50	Registration format. Clinical laboratory determination
Leukocytes	Number of white blood cells per unit volume in venous blood	Number of white blood cells per unit volume in venous blood	Quantitative, Ratio. Quantity per cc Minimum 4,000 Maximum 18,000	Registration format. Clinical laboratory determination

Neutrophils	Granular nucleated leukocytes participating in inflammatory processes.	Number of neutrophilic leukocytes	Quantitative, Ratio. Quantity per cc Minimum 4,000 Maximum 18,000	Registration format. Clinical laboratory determination
Lymphocytes	White blood cells formed by lymphatic tissue.	Number of lymphocytes in blood cell counts	Quantitative, Ratio. Quantity per cc Minimum 1,000 Maximum 8,000	Registration format. Clinical laboratory determination
Fasting Blood Glucose	Glycemia or Glycemia is the amount of glucose or sugar in the blood and is one of the sources of energy for our body, especially for the cells.	Blood sample for blood glucose with eight hours fasting time	Normoglycemia in fasting 70 to 100 mg/dl. Hyperglycemia higher than 100 mg/dl in fasting. Diabetes 126 mg/dl of fasting blood glucose.	Registration form. Blood tests
HbA1c	Measurement of glucose concentration in blood plasma level.	Glycosylated hemoglobin is considered: $HbA1c \geq 6.5\% \text{ (48 mmol/mol)}$ for diagnosis of DM2.	Categorical, Ordinal (%), 6% very low, 7% moderate, 8% high, 9% very high, 10% risk.	Registration form. Blood tests Glycosylated hemoglobin
Insulin	the amount of this hormone insulin in the blood.	Blood sample for insulin with eight hours fasting time	Hyperinsulinemia $>6\mu\text{U}/\text{ml}$	Registration form. Blood tests
Creatinine	Muscle protein degradation product	test that measures the level of creatinine in the blood	Quantitative, Ratio. mg/dl Quantity per cc Minimum 0.4 Maximum 1.3	Registration form. Blood tests
Urea	A substance formed by the body during the metabolism of proteins and nitrogenous compounds in the liver.	test measures the amount of urea in the blood	Quantitative, Ratio. mg/dl Quantity per cc Minimum 8 Maximum 54	Registration form. Blood tests
BUN	Amount of nitrogen from protein metabolism in the blood.	Test that measures the amount of urea nitrogen in the blood.	Quantitative, Ratio. mg/dl Quantity per cc Minimum 8	Registration form. Blood tests

			Maximum 54	
Uric Acid	Uric acid is an organic compound consisting of carbon, nitrogen, oxygen and hydrogen that is formed when purines are broken down by metabolism.	A test that measures the amount of uric acid in the blood.	Quantitative, Ratio. mg/dl Quantity per cc Minimum 2.4 Maximum 9.0	Registration form. Blood tests
Sodium	Electrolytes are minerals present in blood and other body fluids that carry an electrical charge. They affect the amount of water in the body, the acidity of the blood (pH), muscle activity and other important processes.	Determination of the amount of sodium in blood	Quantitative, Ratio. mEq/l Quantity per cc Minimum 135 Maximum 145	Registration form. Blood analysis
Chlorine	Electrolytes are minerals present in blood and other body fluids that carry an electrical charge. They affect the amount of water in the body, the acidity of the blood (pH), muscle activity and other important processes.	Determination of the amount of chlorine in blood	Quantitative, Ratio. mEq/l Quantity per cc Minimum 90 Maximum 110	Registration form. Blood análisis
Potassium		Determination of the amount of Potassium in blood	Quantitative, Ratio. mEq/l Quantity per cc Minimum 3.5 Maximum 5.5	Registration form. Blood análisis

Calcium		Determination of the amount of Calcium in the blood	Quantitative, Ratio. mg/dl Quantity per cc Minimum 8.5 Maximum 10.5	Registration form. Blood análisis
Phosphorus		Determination of the amount of phosphorus in blood	Quantitative, Ratio. mg/dl Quantity per cc Minimum 2.5 Maximum 4.5	Registration form. Blood análisis
Magnesium		Determination of the amount of magnesium in blood	Quantitative, Ratio. mg/dl. Quantity per cc Minimum 1.5 Maximum 2.5	Registration form. Blood análisis
Albumin	Acute phase protein synthesized by the liver.	Amount of this protein in the clear liquid part of the blood.	Quantitative, Ratio. mg/dl. Quantity per cc Minimum 3.4 Maximum 5.4	Registration form. Blood analysis
Direct Bilirubin	A liquid of an oily nature, formed during the destruction of red blood cells, it is secreted by the liver whose function is to digest fatty foods.	Portion of bilirubin conjugated with glucuronic acid, moves freely in the bloodstream.	Quantitative, Ratio Normal value less than 0.3 mg/dl (0 less than 5.1 mcMol/l)	Registration form. Blood analysis

Indirect Bilirubin		Protein-bound portion that requires passage through the hepatocyte.	Quantitative, Ratio unit mg/dl Normal value Minimum 0.1 Maximum 0.5	Registration form. Blood analysis
Total Bilirubin		Sum of Direct B. and Indirect B. Indirect	Quantitative, Ratio unit mg/dl Normal value Minimum 0.1 Maximum 1.2	Registration form. Blood analysis
SGPT Transaminase	Aminotransferases, a group of enzymes that transfer amino groups from one metabolite to another, located mainly in the liver.	Alanine aminotransferase, predominantly hepatic, is released into the bloodstream when the liver is damaged.	Quantitative, Ratio unit IU/l Normal value Minimum 10 Maximum 41	Registration form. Blood analysis
SGOT Transaminase		Aspartate Amino Transferase, an enzyme found in the liver and muscle, is released into the bloodstream when the liver is damaged.	Quantitative, Ratio unit IU/l Normal value Minimum 5 Maximum 37	Registration form. Blood analysis
GGTP		Primarily hepatic enzyme released into the circulation when there is liver damage or biliary tract disease.	Quantitative, Ratio unit IU/l Normal value Minimum 11 Maximum 50	Registration form. Blood analysis

Serum Iron	Essential mineral for the production of hemoglobin, necessary for growth and development.	Test that measures the amount of iron in the blood.	Quantitative , Ratio minimum 60 mcg/dl Maximum 170 mcg/	Registration form. Blood analysis
Total Cholesterol	They are the most common type of fats in the body, coming mainly from saturated fats.	Test designed to measure the amount of free and protein-bound cholesterol in the blood.	Quantitative, Ratio minimum 100 mg/dl Maximum 200 mg/dl	Registration form. Blood analysis
Triglycerides	They are the most common type of fats in the body, coming mainly from saturated fats.	Test designed to measure the amount of triglycerides in the blood.	Quantitative, Ratio Minimum 100 Maximum 500 mg/dl	Registration form. Blood analysis
C HDL	Combination of fats and proteins, necessary for the transport of lipids through the bloodstream.	High Density Lipoproteins	Quantitative, Ratio Greater than 40 mg/dl	
C LDL		Low Density Lipoproteins	Quantitative, Ratio Less than 100 mg/dl	Registration form. Blood analysis

C VLDL		Very Low Density Lipoproteins	Quantitative, Ratio Less than 130 mg/dl	Registration form. Blood analysis
CPK	Enzyme that acts mainly in muscle tissue, brain and heart.	A test that measures the amount of creatinine kinase in the blood is used to diagnose and follow up on muscle injury or damage.	Quantitative, Ratio Muscle damage value less than 200 IU/l	Registration form. Blood análisis
Prot. C Reactive	Circulating plasma protein that increases in levels in response to inflammation, is directly related to IL-6 elevation.	Acute phase reactant protein released into the plasma as a consequence of inflammation.	Quantitative, Ratio less than 10 mg/l	Registration form. Blood análisis
TSH	Thyroid profile is the set of determinations of hormone levels related to thyroid function.	Thyroid stimulating hormone	Quantitative, Ratio 0.3 to 3 IU	Registration form. Blood análisis
T3		Triiodothyronine	Quantitative, Ratio 0.8 to 2 ng/ml	Registration form. Blood analysis
T3 L		Non-protein-bound triiodothyronine	Quantitative, Ratio 2.3 to 4.4 pg/ml	Registration form. Blood análisis
T4		Thyroxine	Quantitative, Ratio 5.4 to 11.5 ng/dl	Registration form. Blood analysis

T4		Thyroxine	Quantitative, Ratio 0.75 to 1.85 ng/dl	Registration form. Blood analysis
Vitamin D	Nutritional co-factor necessary for calcium absorption	cholecalciferol is measured in blood as 25-OH Vit D	Quantitative, Ratio 25 to 90 ng/ml	Registration form. Blood analysis
Gasometric Variables				
PaO2	Partial pressure of oxygen is the measurement of dissolved oxygen particles in the blood expressed in mmHg.	Determine the amount of dissolved oxygen in plasma.	Quantitative, Ratio Unit mmHg Minimum 75 Maximum 100	Registration form. Blood analysis
HCO3	Bicarbonate ion plasma concentration	amount of bicarbonate in blood	Quantitative, Ratio Unit mEq/l Minimum 21 Maximum 30	Registration form. Blood analysis
Arterial pH	Indicates the amount of hydrogen ions contained in the blood.	Determines the degree of acidity or alkalinity of the blood.	Quantitative, Ratio minimum 7.35 maximum 7.45	Registration form. Blood analysis
Lactic Acid	Substance produced by muscle tissue and blood cells. Lactic acid levels increase when oxygen levels decrease.	Acidic substance that accumulates in the blood and causes a decrease in pH, its ionized form is lactate.	Quantitative, Ratio 4.5 to 19 mg/l or 0.5 to 2.2 mmol/liter.	Registration form. Blood analysis
Anion Gap	Difference between anions and cations measured in the serum	Difference between anions and cations measured in serum	Quantitative, Ratio unit mEq/l minimum 8 max. 12	Registration form. Blood analysis
Excess Base	the amount of acid required to return the pH of an individual's blood to a normal value	the amount of acid required to return the pH of an individual's blood to a normal value	Quantitative, Ratio Minimum -2 maximum + 2	Registration form. Blood analysis

Satisfaction and Adherence				
Satisfaction Survey	Positive assessment of the different dimensions of the medical care received	Interrogation Very Satisfied to Very Dissatisfied	Categorical Nominal	Registration form.
Adherence to treatment	Taking medication according to the dosage of the prescribed schedule; and persistence, taking medication over time.	Interrogation Complied or did not comply with the program.	Categorical Nominal	Registration form. adherence to treatment

7.7 Data collection.

All data will be captured and recorded digitally in each of the queries through the Google Forms platform to consolidate the information in Google Sheets.

In the consultation, medical history data will be collected in the form of interrogation, weight will be determined through electronic scales, height through calibrated stadiometers, All measurements will be performed according to the WHO Physical Measurement Guide 2014 (www.who.int/surveillance/steps/Part3_Section4) Annex 1. In addition, a capillary determination of glucose and ketones will be performed at each clinical consultation. Once patients are drawn by lot they will be assigned to one of the control centers distributed in Mexico City, they will always have to go to the same control center (VIME). The consultation visits will be weekly for weight control and clinical check-up and every two weeks alternately for physical and psychological counseling.

Blood samples will be collected in Specialized Clinical Laboratories according to NOM-253-SSA1-2012 and the laboratory sample collection manual in force in each laboratory. A venous sample will be taken to determine Complete Blood Biometry, Blood Chemistry of 27 elements, Basic thyroid profile, Glycosylated

7.8 Measuring instruments.

With all the data, a database will be built in Excel MS®. Patient satisfaction will be measured with the Likert Scale, which consists of 5 possible answers per item: very satisfied, satisfied, indifferent, dissatisfied and very dissatisfied. (attached)

7.9 Statistical analysis.

Descriptive statistical tests will be performed establishing general and group measures, determining variability measures such as standard deviation and Confidence Interval, comparative inferential tests will be performed within and between groups, for quantitative variables it is proposed as an initial T-test, which will be contrasted according to the conditions of normality and homoscedasticity of the sample. For qualitative variables, χ^2 is initially proposed, which will be contrasted according to the same conditions; one-way ANOVA and repeated measures ANOVA will also be used. Microsoft Excel 365 and SPSS V 21

